8.5.1.5 Management of immune related endocrinopathies

New or worsening endocrine disorder.

Endocrine disorder	Action – trial treatment	Recommended management of toxicity
Asymptomatic TSH abnormality	Continue nivolumab treatment at 240mg.	If TSH <0.5xLLN or >2xULN or consistently out of range in 2 subsequent measurements, include free T4 and consider endocrinology opinion.
Symptomatic endocrinopathy (CTCAE G2-3 hypothyroidism, G2-3 hyperthyroidism, G2 adrenal insufficiency, G2-3 hypophysitis, G3 diabetes)	Delay nivolumab treatment. Restart nivolumab at 240mg if/when symptoms improve. If steroids given, patient must have been weaned to ≤10mg per day (or equivalent) before restarting treatment. Maximum permitted delay 4 weeks. Treatment should continue alongside hormone replacement	Refer to Summary of Product Characteristics for detailed guidance on management of individual endocrinopathies. Monitor endocrine function and relevant hormone levels. Steroid treatment as per local policy (recommended dose 1- 2mg/kg/day IV methylprednisolone or equivalent dose of oral steroids). If improves, taper steroids over at least 1 month.

	therapy as long as no symptoms are present.	Hormone replacement as per local policy. Consider prophylactic antibiotics against opportunistic infection.
Severe endocrinopathy (G4 hypothyroidism, G4 hyperthyroidism, G3-4 adrenal insufficiency, G4 hypophysitis,	Permanently discontinue nivolumab treatment.	Refer to Summary of Product Characteristics for detailed guidance on management of individual endocrinopathies.
G4 diabetes)		Monitor endocrine function and relevant hormone levels.
		Steroid treatment as per local policy (recommended dose 1-2mg/kg/day IV methylprednisolone or equivalent dose of oral steroids).
		If improves, taper steroids over at least 1 month.
		Hormone replacement as per local policy.
		Consider prophylactic antibiotics against opportunistic infection.
Suspicion of adrenal crisis e.g. severe hypotension disproportionate to current	Permanently discontinue nivolumab treatment.	Exclude sepsis: give broad spectrum antibiotics if any clinical suspicion.
illness Note: if adrenal crisis is		Manage for Addisonian crisis as per local protocols.
excluded, treat as for symptomatic endocrinopathy.		Consult endocrinologist.

8.5.1.6 Management of renal toxicity

Exclude other causes e.g. nephrotoxicity of concomitant medications, outflow tract obstruction, disease-related causes.

Creatinine elevation CTCAE v5 grade	Action – trial treatment	Recommended management of toxicity
Grade 1 Creatinine >ULN - 1.5xULN	Continue nivolumab treatment at 240mg.	Monitor creatinine weekly If resumes to baseline, resume creatinine monitoring as per section 9.4 (assessments during treatment) If worsens: treat as G2-3 or as G4
Grade 2 Creatinine 1.5xULN - 3xULN	Delay nivolumab treatment.	Closely monitor creatinine levels (recommended every 2-3 days)

Grade 3 Creatinine 3xULN - 6xULN	Restart nivolumab at 240mg if/when returns to ≤G1. If steroids given, patient must have been weaned to ≤10mg per day (or equivalent) before restarting treatment. Maximum permitted delay 4 weeks.	Steroid treatment as per local policy (recommended dose 0.5-1mg/kg/day IV methylprednisolone or equivalent dose of IV steroids). Once improved, taper steroids over at least 1 month. Consult nephrologist and consider renal biopsy. If no improvement after 7 days or worsening after 48 hours: Treat as G4.
Grade 4 Creatinine >6xULN	Permanently discontinue nivolumab treatment	Monitor creatinine levels daily. Steroid treatment as per local policy (recommended dose 1-2mg/kg/day IV methylprednisolone or equivalent dose of oral steroids). Once improved, taper steroids over at least 1 month. Consult nephrologist and consider renal biopsy.

8.5.1.7 Management of neurological toxicity

New or worsening neurological symptoms. Exclude non-inflammatory causes such as infections (encephalitis, meningitis, PML), tumour progression (causing for example cranial nerve or spinal cord compression) or vascular causes (cerebral bleed or infarction).

Grade of neurological toxicity CTCAE v5grade	Action – trial treatment	Recommended management of toxicity
Grade 1 Asymptomatic or mild symptoms not requiring intervention	Continue nivolumab treatment at 240mg.	Monitor closely. If worsens: treat as G2-3 or G4.
Grade 2 Moderate symptoms, limiting instrumental ADL	Delay nivolumab treatment. Restart nivolumab at 240mg if/when returns to ≤G1. If steroids given, patient must have been weaned to ≤10mg per day (or equivalent) before restarting treatment. Maximum permitted delay 4 weeks.	Treat symptoms as per local guidelines. Steroid treatment as per local policy (recommended dose 0.5-1mg/kg/day IV methylprednisolone or equivalent dose of oral steroids). Once improved, taper steroids over at least 1 month. If worsens; treat as G3-4.

Grade 3-4 Severe symptoms limiting self care ADL	Permanently discontinue nivolumab treatment.	Obtain neurology opinion. Treat symptoms as per local guidelines.
		Steroid treatment as per local policy (recommended dose 1-2mg/kg/day IV methylprednisolone or equivalent dose of oral steroids).
		Prophylactic antibodies for opportunistic infections.
		If improves to G2:
		Taper steroids over at least 1 month.
		If worsens or atypical presentation:
		Consider IVIg or other immunosuppressive therapies as per local guidelines.

8.5.1.8 Management of other immune-related adverse reactions

Adequate evaluation should be performed to confirm aetiology and exclude other causes.

See summary of product characteristics for detailed guidance on management of individual toxicities.

CTCAE v5 grade	Action – trial treatment	Recommended management of toxicity
Grade 1	Continue nivolumab treatment at 240mg.	Treatment for symptoms as per local policy.
Grade 2 (first occurrence)	Delay nivolumab treatment Restart nivolumab at 240mg if/when returns to ≤G1. If steroids given, patient must have been weaned to ≤10mg per day (or equivalent) before restarting treatment. Maximum permitted delay 4 weeks.	Treat symptoms as per local guidelines. Steroid treatment as per local policy; taper prior to restarting nivolumab.
Grade 3 (first occurrence – except myocarditis – see below)	Delay nivolumab treatment. Restart nivolumab at 240mg if/when returns to ≤G1. If steroids given, patient must have been weaned to ≤10mg per	Treat symptoms as per local guidelines. Steroid treatment as per local policy; taper prior to restarting nivolumab.

	day (or equivalent) before restarting treatment.	
	Maximum permitted delay 4 weeks.	
Grade 3 myocarditis	Permanently discontinue nivolumab treatment.	Refer for specialist opinion. Manage as per local policy.
Grade 4 or recurrent grade 3;	Permanently discontinue	Treat symptoms as per local
Persistent grade 2 or 3 despite	nivolumab treatment.	guidelines.
intervention;		Steroid treatment as per local
Inability to reduce corticosteroid		policy.
dose to 10mg prednisolone per day or equivalent		Seek specialist opinion.

8.5.2. Recommendations for Treatment of Nivolumab Related Infusion Reaction

As nivolumab is a fully humanised immunoglobulin, it is unlikely to be immunogenic and induce an infusion or hypersensitivity reaction. However, if such a reaction were to occur, it might manifest with fevers, chills, rigors, rash, headache, arthralgia, hypo- or hypertension, bronchospasm. All grade 3 or grade 4 infusion reactions should be reported as an SAE within 24 hours (see section 12.4.4 for details of reporting).

For grade 1 symptoms (Mild reaction, infusion interruption not indicated)

- Remain at bedside and monitor subject until recovery from symptoms.
- Premedication is recommended prior to subsequent infusions. Administration of 10mg IV chlorphenamine and paracetamol 1g PO at least 30 minutes prior to infusion is recommended, but local policies may be followed.

For grade 2 symptoms (Moderate reaction requires therapy or infusion interruption but responds promptly to symptomatic management)

- Stop the nivolumab infusion
- Give supportive care as per local policies. IV infusion of 0.9% sodium chloride solution for injection, and treatment with 1g paracetamol PO, 10mg IV chlorphenamine is recommended. Consider bronchodilator therapy and corticosteroids, up to 25mg IV hydrocortisone is recommended.
- Restart the infusion at 50% of the original infusion rate when symptoms resolve. If no further complications occur after 30 minutes, the rate may be increased to 100% of the original infusion rate. Monitor subjects closely.
- Premedication is recommended prior to subsequent infusions. Use of paracetamol, chlorphenamine and hydrocortisone prior to infusion is recommended, but local policies may be followed.

For grade 3 or 4 symptoms (Grade 3: not rapidly responsive to symptomatic management; recurrence of symptoms following initial improvement) (Grade 4 life threatening; pressor or ventilator support indicated)

- Stop the nivolumab infusion
- Give supportive care as per local policies. An IV infusion of 0.9% sodium chloride solution for injection and treatment with paracetamol, chlorphenamine, bronchodilators (as described for grade 2 reactions above), and 100mg IV methyl-prednisolone or equivalent is recommended.
- Follow institutional guidelines for anaphylaxis if indicated and involve intensive care/critical care outreach teams at an early stage.

Tumour lysis risk

Nivolumab can be associated with tumour lysis syndrome, and patients should be risk-assessed and managed as per local protocols for patients undergoing chemotherapy.

8.5.3. Recommendations for management of pDILI

The diagnostic criteria for pDILI are:

AST or ALT >3 x ULN

and

 Total bilirubin >2 x ULN, without initial findings of cholestasis (elevated serum alkaline phosphatase)

and

 No other immediately apparent causes of transaminase elevation and hyperbilirubinemia, including but not limited to, viral hepatitis, pre-existing chronic or acute liver disease, or the administration of other drug(s) known to be hepatotoxic

There is no specific management for pDILI. If a patient presents with abnormal liver function tests as outlined above, further investigation should be carried out to establish whether the patient has pDILI or autoimmune liver disease.

- Nivolumab should be permanently discontinued.
- Treatment should be given as clinically indicated.
- If autoimmune liver disease is suspected, this should be managed as per section 8.5.1.3 above

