8.4. Dose Modifications

Dose reductions and escalations of nivolumab are **not** permitted. Nivolumab should be delayed for up to 4 weeks for the following:

- Any ≥ grade 3 Haematological toxicity (Hb <80g/dl, platelets <50 x10⁹/l, neutrophils <1.0 x10⁹/l)
- Any ≥ grade 3 drug-related, non–haematological AE **except**:
 - o Fatigue
 - o Alopecia
 - Drug related endocrinopathies adequately controlled with physiologic hormone replacement.
 - Electrolyte disturbances that can be corrected and are unlikely to cause clinical safety concerns.
- Any grade 2 auto-immune complication including pneumonitis, renal dysfunction, diarrhoea/ colitis, neurological complication, derangement of liver function tests. Guidelines for management of auto-immune complications are set out in Section 8.5.
- Any non-drug related AE where the in the local investigator's opinion delaying treatment is in the patient's best interest.

Treatment may be resumed once AEs resolve to grade ≤1 or baseline value. If the criterion to resume treatment is met (see section 8.5), the subject should restart treatment at the next scheduled time-point, as set out in the protocol. If treatment is delayed by >4 weeks, the subject should be permanently discontinued from study therapy. Treatment may be discontinued earlier at the discretion of the investigator if it is felt that continuing on the trial treatment will compromise a successful outcome for the patient.

A treatment summary form must be completed and sent to UCL CTC promptly if treatment is discontinued. The patient will enter follow up as per the trial protocol (see section 9.6.2).

Treatment Discontinuation Criteria

Nivolumab treatment should be permanently discontinued for the following:

 ≥grade 2 drug-related uveitis or eye pain or blurred vision that does not respond to topical therapy. Uveitis is inflammation of the eye, and includes anterior uveitis (synonymous with iritis), posterior uveitis (comprising vitritis, choriditis, retinitis, chroioretinitis) and pan-uveitis (inflammation of the anterior chamber, vitreous, retina and choroid).

- ≥grade 3 pneumonitis
- Any grade 4 drug related AE or laboratory abnormality apart from the following:
 - Grade 4 neutropenia <7 days (G-CSF may be instituted, and continued until neutrophils exceed 1.5x10⁹/L, as per institutional policy)
 - Grade 4 amylase or lipase abnormalities that are not associated with clinical symptoms

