8.5. Management of Adverse Events

8.5.1. Autoimmune complications

Because of its mechanism of action, autoimmune complications are common with nivolumab. Where sites have local policies for management of autoimmune toxicity, these may be followed. Where there is no local policy, suggested guidelines for management of such autoimmune complications are set out below. Clinicians are also advised to refer to the manufacturer's guidelines (see summary of product characteristics).

Autoimmune toxicities are regarded as AEs of special interest for this trial, requiring expedited reporting to UCL CTC. Please refer to section 12.4 for details of how and when to report autoimmune events.

If treatment is delayed by >4 weeks due to autoimmune toxicity, the subject should be permanently discontinued from study treatment.

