8.5.1.3 Management of autoimmune hepatitis

Exclude infective and disease related causes, and hepatotoxicity of other concomitant medications

Hepatitis CTCAE v5 grade	Action – trial treatment	Recommended management of toxicity
Grade 1: AST or ALT >ULN - 3xULN and/or Bilirubin >ULN - 1.5xULN	Continue nivolumab treatment at 240mg.	Continue monitoring of liver function tests as per protocol. If worsening, treat as G2 or G3-4
Grade 2: AST/ALT >3xULN - 5xULN and/or	Delay nivolumab treatment	Increase frequency of monitoring to every 3 days If persists >3 days or worsens:

Bilirubin >1.5xULN - 3xULN	Restart nivolumab at 240mg if/when results improve to baseline. If steroids given, patient must have been weaned to ≤10mg per day (or equivalent) before restarting treatment. Maximum permitted delay 4 weeks.	Steroid treatment as per local policy (recommended dose 0.5-1mg/kg/day IV methylprednisolone or equivalent dose of any oral steroids). If no improvement after a further 3 days, treat as for G3-4. Consider prophylactic antibiotics for opportunistic infections.
Grade 3-4: AST or ALT >5xULN and /or Bilirubin >3xULN	Permanently discontinue nivolumab treatment.	Increase frequency of monitoring to every 1-2 days: Steroid treatment as per local policy (recommended dose 1-2mg/kg/day IV methylprednisolone or equivalent dose of oral steroids). Add prophylactic antibiotics for
		opportunistic infections. Consult gastroenterologist.
		If returns to G2:
		taper steroids over at least 4 weeks
		If not improving after 3-5 days or rebounds:
		give additional immunosuppression as per local policy.

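### For AST/ALT above 3 to 5xULN with bilirubin above 2 to 3xULN, section 8.5.3 stops nivolumab for good, the grade 2 row of 8.5.1.3 allows restart, and the order of precedence is not written down

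*Protocol*

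**What the plan says.** Three places in the Protocol bear on the same laboratory picture.

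- **Section 8.5.3 (pDILI).** The criteria are AST or ALT above 3xULN, total bilirubin above 2xULN without cholestasis, and no other immediately apparent cause. For a patient presenting this way, "further investigation should be carried out to establish whether the patient has pDILI or autoimmune liver disease". A list of actions follows. The first is "Nivolumab should be permanently discontinued"; the last is "If autoimmune liver disease is suspected, this should be managed as per section 8.5.1.3 above".
- **Section 8.5.1.3 (autoimmune hepatitis), grade 2 row.** This covers AST/ALT above 3 to 5xULN and/or bilirubin above 1.5 to 3xULN. In the column for action on trial treatment it says to delay and then "Restart nivolumab at 240mg if/when results improve to baseline", provided any steroids are down to 10mg per day or less and the delay is at most 4 weeks. Permanent discontinuation begins only in the grade 3-4 row (AST/ALT above 5xULN and/or bilirubin above 3xULN).
- **Section 8.4 (dose modifications).** The reasons for delay include "Any grade 2 auto-immune complication including pneumonitis, renal dysfunction, diarrhoea/ colitis, neurological complication, derangement of liver function tests". Treatment may be resumed after recovery, and on timing: "If the criterion to resume treatment is met (see section 8.5), the subject should restart treatment at the next scheduled time-point". The section's list of reasons for permanent discontinuation does not name pDILI.

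On status, section 8.5.1 lets sites follow local policy for autoimmune toxicity. Where there is none, "suggested guidelines for management of such autoimmune complications are set out below".

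**The concern.** Section 8.5.3 attaches the permanent stop to the presenting laboratory values, while the cause is still to be established. If autoimmune disease is then suspected, it refers the clinician to a table that has its own column for what to do with nivolumab. For grade 2 values that column allows restart. The referral does not say whether it covers the whole row or only the treatment of the liver toxicity.

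A clinician who starts from 8.5.1.3 or from the lists in 8.4 meets no reference to 8.5.3. Section 8.4 ties resumption to section 8.5, but section 8.5 contains both answers. At stake is re-exposure to nivolumab after a combined rise in transaminase and bilirubin that the protocol elsewhere treats as a reason to stop for good, and different handling of identical patients at different sites.

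**Working it through.** The protocol states no figure to reproduce. The check is whether the two sets of thresholds overlap, and where.

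**Inputs**, in multiples of ULN, for a patient without cholestasis or another apparent cause:

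- pDILI (8.5.3): AST/ALT > 3 **and** bilirubin > 2.
- Grade 3-4 (8.5.1.3): AST/ALT > 5 **or** bilirubin > 3.
- Grade 2 (8.5.1.3): not grade 3-4, and AST/ALT > 3 **or** bilirubin > 1.5. This takes the worse of the two bands as the grade, which the table's and/or wording implies.

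**Overlap.** Removing the grade 3-4 region from the pDILI region leaves 3 < AST/ALT ≤ 5 with 2 < bilirubin ≤ 3. Every point there is grade 2, since AST/ALT exceeds 3. Every other pDILI point is grade 3-4, where both sections stop nivolumab permanently. The conflict is confined to that window.

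| AST/ALT | Bilirubin | 8.5.3 criteria | 8.5.1.3 row | Action on nivolumab |
|---|---|---|---|---|
| 4 | 2.5 | met | grade 2 | permanent stop against delay and restart |
| 6 | 2.5 | met | grade 3-4 | both stop |
| 4 | 3.5 | met | grade 3-4 | both stop |
| 4 | 1.8 | not met | grade 2 | delay and restart only |
| 2.5 | 2.5 | not met | grade 2 | delay and restart only |

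**At entry.** Section 6.2.3 requires AST/ALT below 2.5xULN and bilirubin below 1.5xULN for trial treatment. No eligible patient is in the window at the eligibility test, so the conflict concerns values that arise afterwards.

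**Does another section settle it?** Sections 12.1, 12.2.2 and 12.4.2 name pDILI for reporting only and give no action on the drug. No section states an order of precedence.

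**The case against.** The strongest reply is that 8.5.3 already gives a workable answer. Its bullets apply to one patient. The first stops the drug without condition, and the last speaks of managing the liver disease. To read the last as permission to restart would empty the first. Section 8.5.3 is also the more specific rule, since it needs both rises and excludes other causes, whereas grade 2 needs only one rise. This is the better reading, and it stands. A reader might infer that the protocol gives opposite orders with no way to choose between them; the text does not support that. What remains is that the reading is unwritten and cannot be seen from 8.5.1.3.

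Three other stronger readings also fail:

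- **That 8.4 orders resumption.** Its wording on resuming is permissive, its sentence on restarting sets the timing once the criterion is met, and it lets the investigator discontinue earlier. A site that stops under 8.5.3 does not breach it.
- **That pDILI's absence from the 8.4 discontinuation list shows a restart is intended.** The list also omits stops that 8.5.1 does contain, such as grade 3 hepatitis and grade 3 colitis, so it is not exhaustive.
- **That the grade 2 escalation sentence ("If no improvement after a further 3 days, treat as for G3-4") removes the restart for slow improvers.** It stands in the column on managing toxicity, not the column on trial treatment, and does not say that the drug action changes.

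The safeguards are real. Restart requires a return to baseline, low-dose steroids at most, and a delay within 4 weeks. Section 12.4.2 requires an SAE report within 24 hours of diagnosis, and section 14.1 escalates apparent departures from the dose modification rules. They limit harm, but they do not say which action applies to a patient who returns to baseline in time.

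**Conclusion.** The point holds as a minor safety clarification. In one window (AST/ALT above 3 to 5xULN with bilirubin above 2 to 3xULN, non-cholestatic, no other apparent cause) the printed actions on nivolumab differ. The intended precedence, most likely that the 8.5.3 stop prevails, is left to inference.

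The size is small. The protocol plans to treat 30 patients for at most 8 cycles and gives no frequency for this laboratory pattern, so no expected number of cases can be stated. The 8.5.1 tables are advisory and yield to local policy, and 8.5.3 is itself headed as recommendations. No effect on the primary endpoint is claimed. The conclusion assumes only that the hepatitis grade is the worse of the two laboratory bands.

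**What to change.** Add to 8.5.3, with a cross-reference in the grade 2 row of 8.5.1.3, a sentence to this effect: if the pDILI criteria are met, permanent discontinuation overrides the grade 2 restart, and section 8.5.1.3 then applies to toxicity management only. Add pDILI to the permanent discontinuation list in 8.4.

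This needs no extra tests or visits. The cost is that a few patients in the window who prove to have grade 2 autoimmune hepatitis could not resume nivolumab. If the sponsor wants them to be able to restart once autoimmune hepatitis is confirmed, 8.5.3 should say so as an explicit exception.

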8.6. Management of Overdoses, Trial treatment error or Occupational Exposure

Overdose

Administration of a quantity of a trial treatment, either per administration or cumulatively, which is in excess of the protocol specified dose. The dose can either be evaluated as overdose by the trial team at site or by the Sponsor upon review.

No specific information is available on the management of nivolumab overdose. The patient should be carefully monitored and supportive care instituted as appropriate.

Any overdoses require expedited reporting to UCL CTC as an SAE (see section 12.2.212.2.2 (Reporting of serious adverse events) for reporting procedures).

Any overdoses must also be reported as an incident according to the instructions in section 13.1 (Incident reporting).

See also section 12.4.3 (Overdoses).

Trial treatment error

Any unintentional error in prescribing, dispensing, or administration of a trial treatment while in the control of a healthcare professional or consumer. The error can be identified either by the trial team at site or by the Sponsor upon review.

Include details from IB/SPC on the clinical management of trial treatment errors, where available. Trial Treatment errors should be reported on in incident report (see section 13.113.1). Any adverse events resulting from a medication error should be reported as an SAE (see section 12.2.212.2.2 for reporting procedures).

Occupational exposure

Exposure to a trial treatment as a result of one's professional or non-professional occupation. Occupational exposure should be reported on an incident report form (see section 13.143.1).

